4. How feasible and acceptable are the strategies to participants, and what are the barriers and facilitators to sustained cessation during the trial period? How are the relapse prevention strategies used, and are patterns of use related to cessation outcomes? (Explorative analyses of EMA/qualitative sub study data complementing cessation reports at follow-ups; quantitative analysis will not be possible in the curtailed trial.)
5. What are the rates of negative aspects (adverse events) reported in people who use a smoking replacement product compared to those who do not and does this vary by type of product used?

Primary Outcome

Original

Sustained abstinence between 1 and 12 months post quit date, with no reported relapse (7 or more days of continuous smoking) and no smoking at all in the last month, biochemically verified.

Curtailed Trial

Sustained abstinence (i.e. no relapse) between 1 and 6 months post quit date. Relapse is defined as 7 or more days of continuous smoking reported at any follow up or any cigarettes smoked (even just a puff) in the last month at 6 months. Abstinence will be based on self-report as no biochemical validation was planned at 3- or 6-month follow-up.

Original Secondary Outcome

1a. Sustained abstinence using different criteria for the primary outcome (e.g. 6 months sustained abstinence according to Russel Standard definition) and different assumptions about missing cases.

1b. Point prevalence abstinence at 3 and 6 months and shorter-term period prevalence outcomes

1c. Sustained reduction in cigarette consumption of at least 50% from baseline in those who do not achieve abstinence at 6 months.

2. Evaluations of likely mechanisms of effect in particular focusing on these strategies that were encouraged and participant perceptions of effect (e.g. participant ratings), including use of EMA/qualitative sub studies

3. Dose response effects - is the dose of the interventions, or extent of compliance, associated with relapse

4. Effects of intervention components (e.g. on relapse rates, participant ratings etc.) by country and on people from different socioeconomic and ethnic groups, of different gender, with different prior smoking habits, and those who stopped smoking using different forms of medication

5. Cost-effectiveness of the different strategies

Curtailed Trial Secondary Outcome

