1a. Sensitivity analyses using different criteria to define abstinence, e.g. Russel Standard, defined as not smoking more than 5 cigarettes since 2-weeks post quit date. Sensitivity analyses using different approaches to imputed missing smoking status at 6 months; specifically, multiple imputation by chained equation and complete case analysis

1b: Point prevalence abstinence at 3- and 6-months, defined as no smoking (not even a puff) in the past seven days.

1c. Sustained reduction in cigarette consumption, defined as at least 50% reduction in cigarettes smoked per day (or week if originally non-daily smoker) from baseline in those who do not achieve abstinence at 6 months.

2. Evaluations of likely mechanisms of effect in particular focusing on these strategies that were encouraged and participant perceptions of effect (e.g. participant ratings), including use of explorative EMA/qualitative sub studies, e.g. using the EMA data, we will compare the characteristics of lapses across the four groups. Using multilevel models, characteristics of smoking lapses (triggers, levels of craving and withdrawal etc.) will be compared across the four treatment groups.

3. Rates of adverse events/serious adverse events (using MedDRA terminology) reported in people who use a smoking replacement product compared to those who do not and by type of product used.

Qualitative sub study

Original trial

At 3, 6- and 12-months post QD a sub sample of participants who had relapsed, lapsed, or remained abstinent will be invited to take part in a qualitative interview (N=160 in total, split equally between the 2 countries and 4 arms).

Curtailed trial

The qualitative study will provide data on the likely mechanisms of effect from ~100 participants who have and have not relapsed, and including lapsers, in the control and intervention arms from both countries, at 3 and 6 months. The following concepts will be looked at:

1. Feasibility, acceptability, use and perceived impact of study processes and interventions
2. How do lapses influence relapse?
3. Barriers and facilitators to maintaining abstinence
4. Cross-cultural perspectives, between UK and Australia, on cessation and relapse prevention support

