They will be offered a version of the text messaging program without the specific strategies focused on in the S3P intervention. They will not be provided with any SR products (although they may be using them as part of their continued UC at the SSS).
- 2. Only SR:** This group will be offered a SR product. Participants will choose one SR product from up to three NRT and EC options (two fast acting NRT and one EC) to use as a coping strategy if at risk of relapse.
- 3. S3P / No SR arm:** After answering some additional questions participants will receive an initial personalised, tailored plan, focusing on S3P (Structured Planning and Prompting Protocol) strategies, and access to a tool designed to help them form implementation intentions for situational temptations to smoke (Problem Planner). These will be reinforced with additional text messages that will remind them to rehearse these self-statements, replacing and extending the more general messages used in the UC condition. These resources will be available to them on the internet for future use, with prompts to use when recommended (around the time of stopping base medication or when having additional problems).
- 4. S3P plus SR arm:** Participants will receive both interventions, with S3P modified to include integrated references to SR as a relapse prevention strategy.

Curtailed Trial Follow-up (no 12-month follow-up)

Participants will complete online questionnaires at 3 and 6 months post-QD (approximately 2- and 5-month post-recruitment) for smoking status and other measures. Participants will be contacted by telephone to complete the questionnaires if they prefer, or if they do not respond to the email prompts to complete them. Participants will receive £10 (UK)/\$20 (Australia) for completing the questionnaires at 3 and 6 months.

Although the research team had telephone contact with some participants at 3 and 6 months to assess outcomes no counselling was provided at these follow-up calls.

NB. Participants who did not want to use a nicotine based product were not randomised into the study, but were offered access to the S3P program, and were followed up passively only (i.e. they received email reminders to complete the follow up questionnaires online, but were not actively followed up by the study team). The analysis of this subsidiary study is not included in this SAP.

Curtailed Measures

Baseline:

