Curtailed Trial Sample Size

The analysis plan is for the curtailed trial. The study was originally powered to be able to assess the effectiveness of the SR and S3P interventions (main effects); SR (2 arms) vs. no SR (2 arms) & S3P (2 arms) vs. no S3P with power = .90 and $\alpha = 0.025$.

With a final sample size of 235 and using $\alpha 0.025$, we have 30% power to detect a difference between arms (i.e. S3P vs no S3P or SR vs no SR), if one really exists. If we wanted to compare the 4 arms simultaneously in 1 model, the analysis would have 51% power with $\alpha 0.05$ (one-sided).

An alternative approach is to consider the study arms as an ordinal measure where participants are allocated to 0 (UC), 1 (S3P or SR arm), or 2 interventions (S3P+SR). We can assess whether the number of interventions received affects continued abstinence. With a final sample size of 235 and $\alpha = 0.05$ one-sided we have 78% power and this would also avoid multiple testing. We expect the intervention to be more effective at 12 months and, therefore, this is an optimistic power estimate but we can't estimate to what degree.

Overall, the latter approach offers us a viable option to explore differences in therapy on smoking relapse. The revised analyses for the curtailed trial will be useful for future meta-analysis looking at the impact of smoking replacement and/or Structured Planning and Prompting Protocol (S3P) on relapse.

ANALYSIS PLAN

Descriptive statistics

Participants' characteristics at baseline and follow-up will be presented broken down by all 4 arms using appropriate descriptive statistics; mean and standard deviation for continuous measures that are approximately symmetric; median and quartiles if they are skewed distributions. Discrete outcomes should be described using both the number and proportion (percentage). Similarly, summary measures of the primary (i.e. quit rates) and secondary outcomes by arms will also be presented.

Analysis of primary and secondary outcomes

Analyses for the primary and secondary outcomes will use the intention-to-treat (ITT) approach. All participants will be included in the analysis and will be analysed according to the treatment group to which they were randomised. All participants with missing outcomes at six months will be considered to be smoking (relapsed) as per Russell Standard, and to have not reduced their number of cigarettes smoked per day from baseline.

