All analyses will be conducted using a logistic regression where relapse status is regressed onto an ordinal predictor which codes the number of active interventions assigned (0, 1, or 2) adjusted for the stratified (i.e. country). A likelihood ratio test will be conducted initially to assess whether the ordinal predictor should be modelled as continuous or categorical. If the treatment effect is positive, we will also explore the moderating role of country on the treatment effect by including an interaction term between 'treatment' and country. Estimates and 95% confidence intervals will be presented.

Sensitivity analyses of the primary outcome

To assess the robustness of the results, a series of sensitivity analyses will be conducted using different approaches to impute missing information; specifically, we will use multiple imputation by chained equation [26] and complete case analysis where we exclude cases with missing outcomes. To build the multiple imputation model, we will explore differences in baseline measures between participants with complete and missing outcome measures.

Sensitivity analyses will also explore alternative definition of sustained abstinence for the primary outcome, e.g. Russel standard defined as not smoking more than 5 cigarettes since 2-weeks post quit.

Lastly, per protocol analysis will also be conducted to exclude those participants who were not using their allocated product. This will allow us to assess the robustness of the results following departures from the randomised treatment.

No statistical testing (p -value) will be reported for the sensitivity analyses as we are mostly interested in assessing how robust the results are.

All analyses will be carried out in Stata.

Number needed to treat

The number needed to treat (95%CI) for one additional person not to relapse will also be estimated.

Adverse events

The number of adverse events and serious adverse events by study arm will be presented and specific events will be listed.

Tables to be included

- Descriptive statistics of baseline characteristics by study arm.
- Proportion of missing information on the primary and secondary outcomes by study arm.

- Differences in baseline characteristics between patients with complete vs. missing information on the primary outcome.

Figures to be included

- CONSORT diagram

References

1. Ferguson, J., et al., *The English smoking treatment services: one-year outcomes*. *Addiction*, 2005. **100**(s2): p. 59-69.

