- Reminded myself of my reasons for quitting
- Distracted myself by doing something else
- Put in place a plan I had for resisting
- Just tried to ignore it
- Just waited until the craving went away
- Told myself that I am beating my addiction
- Some other strategy. If other, please specify the other strategy:

3 and 6 month survey:

Do/Did you make a list of your reasons for quitting?

1. Yes, and I remind myself whenever I feel the need
2. Yes, but I never look at it these days
3. No

OR:

Did you make a list of your reasons for quitting?

1. Yes, and I kept reminding myself of it up to the time I relapsed
2. Yes, but I wasn't using it at the time I relapsed
3. No

3 and 6 month survey:

Have/Had you been giving yourself rewards for achieving milestones? (e.g. spending some of the money you have saved on something nice)

1. Yes
2. No

3 and 6 month survey:

How useful do you think the QuitCoach has been [was] in helping you stay quit?

1. Very useful
2. Somewhat useful

3. Neither
4. Somewhat useless
5. Very useless

3 month survey:

Do you plan to visit the QuitCoach again?

1. Yes
2. Not sure
3. No

3 and 6 month survey:

How useful do you think the text messages have been in helping you stay quit?

1. Very useful
2. Somewhat useful
3. Neither
4. Somewhat useless
5. Very useless

Adverse events/serious adverse events

3 and 6 month survey:

Have you experienced any **new** health problems, or worsening of existing health problems since you joined this study?

Yes/No

Please list the new/worsened health problems you have experienced (list up to 3 problems):

Problem 1: _____

Has the health problem stopped you from doing things you would normally do?

1) No 2) A little 3) A lot

Are/were any of these health problems serious (e.g. life threatening, resulted in hospitalisation, resulted in ongoing or significant disability/incapacity, or otherwise considered significant)?

1. Yes
2. No

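### The safety outcome is defined by actual use of smoking replacement and by product, but the plan only counts events by arm, and the survey items do not fully support those counts

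*SAP*

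**What the plan says.** - **Outcome.** SAP, item 3 of the Curtailed Trial Secondary Outcome list: "Rates of adverse events/serious adverse events (using MedDRA terminology) reported in people who use a smoking replacement product compared to those who do not". The same item asks for a split by product type. Curtailed secondary objective 5 poses the same question: "reported in people who use a smoking replacement product compared to those who do not and does this vary by type of product used".
- **Analysis.** SAP, Adverse events: "The number of adverse events and serious adverse events by study arm will be presented and specific events will be listed".
- **Analysis set.** SAP, Analysis of primary and secondary outcomes: "Analyses for the primary and secondary outcomes will use the intention-to-treat (ITT) approach".
- **Use versus allocation.** SAP, Randomisation Procedures: usual-care participants are not given smoking replacement (SR) products, "although they may be using them as part of their continued UC at the SSS". Participants in the SR arm pick their own product from up to three.
- **Source.** Appendix 1 names the 3- and 6-month surveys as the adverse event source. Both ask about new problems, "or worsening of existing health problems since you joined this study". Up to three problems can be listed. Seriousness is then a single yes/no item: "Are/were any of these health problems serious".

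**The concern.** The outcome and the analysis answer different questions. The first concerns people who used a product; the second concerns people assigned to an arm. A statistician following the Adverse events section would never produce the result that objective 5 asks for. One following objective 5 would have to invent a definition of a user and then compare self-selected groups.

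The unit being counted is also weakly defined. An event count by arm needs a rule for deciding when two reports are one event and which listed problems are serious. The SAP gives neither. Without a matching rule, the count depends partly on who answered both surveys, because only those people can report the same problem twice. If response differs between arms, part of an apparent difference in events could be an artefact. The SAP says the results are meant to be useful for later meta-analysis, so the safety counts should be reproducible.

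**Working it through.** The SAP states no adverse event figure, so there is nothing to reproduce. The check sets the sections side by side and adds two illustrations on assumed inputs.

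**1. Outcome against analysis.** Item 3 needs a rate, a split by use and a split by product. The Adverse events section offers a number, a split by arm and a listing. Neither that section nor Tables to be included mentions a table by use or by product, and no rule defines a user. The only model described regresses relapse status.

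**2. Are the stated contrasts randomised?** No. Non-allocated use is possible under usual care. The exclusion criteria remove current e-cigarette or oral nicotine replacement users only if they plan more than 3 months of use. SR is offered as something to turn to when relapse threatens, so use is linked to relapse risk. The participant chooses the product.

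**3. How far apart can the two analyses be?** Let u1 be the share using SR in the SR arms and u0 the share in the other arms. If events depend only on use, then

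by-arm difference ÷ user-versus-non-user difference = u1 − u0.

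The SAP gives neither share. Assumed range: u1 from 0.6 to 1.0, u0 from 0 to 0.4.
- Smallest: 0.6 − 0.4 = 0.2
- Middle: 0.8 − 0.2 = 0.6
- Largest: 1.0 − 0 = 1.0

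The by-arm difference is thus 20% to 100% of the other, so one cannot stand in for the other.

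**4. Repeat reports.** The appendix's items on smoking since the last survey look back only to that survey, while the adverse event item looks back to study entry both times. Let s be the share of all events occurring before the first survey and r the probability that such an event is reported again at 6 months. The first survey yields the early events; the second yields the late events plus the repeats. If everyone answers both surveys and the three-problem limit does not bite, the unmatched sum exceeds the true total by s × r.

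The surveys fall about 2 and 5 months after recruitment, so a constant event rate gives s = 2/5 = 0.40. An assumed front-loaded pattern takes s = 0.60.

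| r | s = 0.40 | s = 0.60 |
|---|---|---|
| 0.25 | 10% | 15% |
| 0.50 | 20% | 30% |
| 1.00 | 40% | 60% |

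For one persisting problem the ceiling is two-fold; for the total it is 1 + s.

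**5. Serious events.** Suppose a participant lists k problems (1 to 3) and answers yes on seriousness. The number of serious problems is then between 1 and k. With k = 1 it is known; with k = 2 or 3 neither the number nor the identity is known. Whether a participant had any serious problem is known for every k. By contrast, interference with normal activities is asked about the individual listed problem.

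**The case against.** The case on the other side has several sound parts.

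- **The specified analysis is randomised.** Events are to be tabulated by arm, under intention to treat, and adding arms gives SR versus no SR. A reader might infer that the trial's safety answer would rest on the confounded user comparison. The SAP does not support that: it specifies no user comparison at all. The defect is the mismatch.
- **Duplication is not automatic.** A reader might infer that the survey items necessarily double-count. They do not. A problem must be reported again and the two surveys summed without matching, and the SAP does not say they will be summed. Free-text entries, MedDRA terms and an event listing make matching feasible. What stands is that no matching rule is given.
- **Serious events are often identifiable.** A reader might infer that they never are. With one listed problem they are, and affected participants can always be counted. Fuller capture of serious events may also be set out in the protocol, which is not at hand. Even so, Appendix 1 names the surveys as the source for this outcome.
- **Percentages and missingness are promised.** Descriptive statistics calls for numbers and proportions for discrete outcomes, and Tables to be included has missingness by arm. It would be wrong to say that the plan ignores non-response. But a percentage of events has no clear base when one person can contribute several, and the missing-outcome rule covers only smoking status and reduction.
- **A use-based question is legitimate.** Use, including non-allocated use, is collected at follow-up, and no test is attached to it. It should stay, correctly labelled.

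**Conclusion.** The point holds in a limited form. The stated safety outcome has no matching analysis, and the analysis that is planned uses a unit, the event, that the named source supports only partly. Early problems can be counted twice if the surveys are summed without matching. The number of serious events cannot be derived when a participant lists more than one problem and answers yes on seriousness.

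The mismatch and the wording of the survey items rest on the text alone. The sizes do not: the 10% to 60% inflation and the 20% to 100% ratio depend on assumed event timing, re-reporting and use, and only show what is possible. The effect is confined to safety reporting. No primary result, power figure or test changes. It is worth correcting before the safety tables are produced.

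**What to change.** Reword the Adverse events section as follows.

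1. **Main table.** Give the number and percentage of participants with at least one adverse event, and with at least one self-reported serious adverse event, across the two surveys. Show this by the four arms and by randomised SR versus no SR (about 235 ÷ 2 = 117 or 118 a side if allocation was even).
2. **Denominators.** Show both the number randomised and the number answering an adverse event item at each survey. Neither is enough alone: the first treats non-responders as event-free, and responders to at least one survey have either about 2 or about 5 months covered.
3. **Repeat reports.** Match reports of the same problem across surveys before any event count or listing.
4. **Seriousness.** Report serious events at participant level. Where several problems are listed with a yes, mark in the listing that the serious one is not identified.
5. **Use and product tables.** Define use, present these tables to answer objective 5, and label them descriptive and non-randomised.

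The cost is SAP wording and a matching step during MedDRA coding; no new data are needed. The drawback is that participant-level counts do not show recurrences, which the matched event listing can still show.

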Sustained abstinence (i.e. no relapse) between 1 and 6 months post quit date. Relapse is defined as 7 or more days of continuous smoking reported at any follow up or any cigarettes smoked (even just a puff) in the last month at 6 months.	
6 month survey:
 
Have you smoked at all since we last surveyed you on <inset date>?
 
 1. No, not even a puff 2. Yes – just a few puffs 3. Yes – 1- 5 cigarettes in total 4. Yes – more than 5 cigarettes in total 
When did you last smoke a cigarette?
 
 1. Today 2. Yesterday 3. 2-6 days ago 4. 1-2 weeks ago 5. More than 2 weeks to 30 days (1 month) ago 6. More than 1 month ago 
3 and 6 month survey:
 
At any time since <last survey> did you smoke every day for a week or more?
 
 1. Yes 2. No

Secondary outcomes

Outcome and definition	Data source
Sensitivity analyses using different approaches to imputed missing smoking status at 6 months;	
6 month survey:
 
Have you smoked at all since we last surveyed you on <inset date>?
 
 1. No, not even a puff 2. Yes – just a few puffs

specifically, multiple imputation by chained equation.
	
 3. Yes – 1- 5 cigarettes in total 4. Yes – more than 5 cigarettes in total 
When did you last smoke a cigarette?
 
 1. Today 2. Yesterday 3. 2-6 days ago 4. 1-2 weeks ago 5. More than 2 weeks to 30 days (1 month) ago 6. More than 1 month ago 
3 and 6 month survey:
 
At any time since <last survey> did you smoke every day for a week or more?
 
 1. Yes 2. No

Point prevalence abstinence at 3 months, defined as no smoking (not even a puff) in the past seven days
	
3 month survey:
 
Have you smoked at all since we last surveyed you on <inset date>?
 
 1. No, not even a puff 2. Yes – just a few puffs 3. Yes – 1- 5 cigarettes in total 4. Yes – more than 5 cigarettes in total 
3 month survey:
 
When did you last smoke a cigarette?
 
 1. Today 2. Yesterday 3. 2-6 days ago 4. 1-2 weeks ago 5. More than 2 weeks to 30 days (1 month) ago 6. More than 1 month ago


Point prevalence abstinence at 6 months, defined as no smoking (not even a puff) in the past seven days
	
6 month survey:
 
Have you smoked at all since we last surveyed you on <inset date>?
 
 1. No, not even a puff 2. Yes – just a few puffs 3. Yes – 1- 5 cigarettes in total 4. Yes – more than 5 cigarettes in total 
6 month survey:
 
When did you last smoke a cigarette?
 
 1. Today 2. Yesterday 3. 2-6 days ago 4. 1-2 weeks ago 5. More than 2 weeks to 30 days (1 month) ago 6. More than 1 month ago

Sustained reduction in cigarette smoking at 6 months in those who do not achieve abstinence. Defined as a 50% (or greater) reduction in cigarettes smoked (either per day or per week) at from baseline to 6 months post quit
	
6 month survey:
 
How many cigarettes do you currently smoke per day (OR per week if nondaily smoker)

6 month sustained abstinence according to the Russel standard, defined as smoking no more than 5 cigarettes since 2 weeks post target quit date
	
Baseline survey:
 
Have you smoked as much as a puff of a cigarette since you quit?
 
 1. No, not even a puff 2. Yes – just a few puffs 3. Yes – 1- 5 cigarettes in total 4. Yes – more than 5 cigarettes in total 
When did you last smoke?
 
 1. Earlier today 2. Yesterday 3. 2-3 days ago 4. 4-7 days ago 5. 8-14 days ago 6. More than 2 weeks ago 
3 and 6 month survey:
 
Have you smoked at all since we last surveyed you on <inset date>?
 
 1. No, not even a puff 2. Yes – just a few puffs

- | | |
|--|--|
| | 
3. Yes – 1- 5 cigarettes in total4. Yes – more than 5 cigarettes in total |
|--|--|

Evaluations of likely mechanisms of effect in particular focusing on these strategies that were encouraged and participant perceptions of effect (e.g. participant ratings), including use of EMA/qualitative sub studies.

3 and 6 month survey:

Thinking about the period before you returned to smoking.] We are interested in the extent to which you may have done certain things to help you stay quit.

When you [If M3_SMKSTAT=2: have been/ If M3_SMKSTAT=1: were] strongly tempted to have a cigarette, which of the following [If M3_SMKSTAT=2: have you done/ If M3_SMKSTAT=1: did you do] regularly? (YES/NO)
(YES/NO)

- Reminded myself of my reasons for quitting
- Distracted myself by doing something else
- Put in place a plan I had for resisting
- Just tried to ignore it
- Just waited until the craving went away
- Told myself that I am beating my addiction
- Some other strategy. If other, please specify the other strategy:

3 and 6 month survey:

Do/Did you make a list of your reasons for quitting?

1. Yes, and I remind myself whenever I feel the need
2. Yes, but I never look at it these days
3. No

OR:

Did you make a list of your reasons for quitting?

1. Yes, and I kept reminding myself of it up to the time I relapsed
2. Yes, but I wasn't using it at the time I relapsed
3. No

3 and 6 month survey:

Have/Had you been giving yourself rewards for achieving milestones? (e.g. spending some of the money you have saved on something nice)

1. Yes
2. No

3 and 6 month survey:

How useful do you think the QuitCoach has been [was] in helping you stay quit?

1. Very useful
2. Somewhat useful

3. Neither
4. Somewhat useless
5. Very useless

3 month survey:

Do you plan to visit the QuitCoach again?

1. Yes
2. Not sure
3. No

3 and 6 month survey:

How useful do you think the text messages have been in helping you stay quit?

1. Very useful
2. Somewhat useful
3. Neither
4. Somewhat useless
5. Very useless

Adverse events/serious adverse events

3 and 6 month survey:

Have you experienced any **new** health problems, or worsening of existing health problems since you joined this study?

Yes/No

Please list the new/worsened health problems you have experienced (list up to 3 problems):

Problem 1: _____

Has the health problem stopped you from doing things you would normally do?

1) No 2) A little 3) A lot

Are/were any of these health problems serious (e.g. life threatening, resulted in hospitalisation, resulted in ongoing or significant disability/incapacity, or otherwise considered significant)?

1. Yes
2. No
